### 2.2 Secondary objective(s)

1. To evaluate between-treatment differences for the change in LS-BMD Z-score at Month 6 relative to baseline.
2. To evaluate between-treatment differences for the change in LS and total body BMC at 6 and 12 months.
3. To evaluate between-treatment differences for the change in serum P1NP, BSAP, NTX, and TRAP-5b at Month 6 and Month 12 relative to baseline.
4. To evaluate between-treatment differences for the proportion of patients with new vertebral fractures at Month 12 relative to baseline.
5. To evaluate the between-treatment differences for change in vertebral morphometry at Month 12 relative to baseline.
6. To evaluate the between-treatment differences for change in pain using the Faces Pain Scale-Revised (FPS-R) at Months 3, 6, 9 and 12 relative to baseline.
7. To evaluate the between-treatment differences for change in 2nd metacarpal cortical width at Month 12 relative to baseline.
8. To measure urinary concentration of zoledronic acid at Month 12.
9. The safety objective is to demonstrate that zoledronic acid is safe for the treatment of osteoporotic children treated with glucocorticoids through the monitoring of relevant clinical and laboratory safety parameters.

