### 9.4.2 Statistical model, hypothesis, and method of analysis

The primary efficacy objective is to demonstrate superiority with respect to the change in LS-BMD Z-score at Month 12 relative to baseline in patients treated with zoledronic acid compared to patients receiving placebo.

Let  $\mu_Z$  and  $\mu_P$  be the population mean of the change in LS-BMD Z-score at Month 12 relative to baseline for patients treated with ZOL and patients receiving placebo, respectively. The null hypothesis of no difference between treatment groups ( $H_0 : \mu_Z = \mu_P$ ) will be tested against the alternative hypothesis that there is difference between treatment groups ( $H_A : \mu_Z \neq \mu_P$ ). The tests will be done at a nominal significance level of  $\alpha = 0.05$ .

The primary efficacy objective will be demonstrated by showing that the t test statistic,  $\frac{|d|}{SE}$ , is greater than  $t_{df,0.975}$  in the modified intent-to-treat population, where  $d$  and  $SE$  are the estimated treatment difference and the estimated standard error of  $d$  from an analysis of covariance (ANCOVA) model with treatment, pooled centers, underlying condition treated with glucocorticoids and baseline LS-BMD Z-score as explanatory variables,  $df$  is the associated degrees of freedom computed from the error term in the model, and  $t_{df,0.975}$  is the

97.5% quantile of the  $t$  distribution with  $df$  degree of freedom. The test and confidence intervals based on this test statistic are robust to the assumptions of normality and of equal variances when within-center treatment group sample size are equal, which is generally the case that treatment allocation is nearly equal within each center because of the manner in which the randomization is carried out. Nevertheless, the underlying assumption of normality and variance homogeneity for the primary analyses will be reviewed and tested by Shapiro's test and Levene's test, respectively, prior to unblinding the data. If the underlying assumption is violated, a transformation or non-parametric approach, such as van Elteren or Cochran-Mantel-Haenszel test (CMH2 from SAS procedure PROC FREQ) adjusted for center, will be applied to the data as appropriate for the hypothesis evaluated.

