## 9.8 Sample size calculation

The sample size is calculated to show superiority of zoledronic acid relative to placebo at Month 12.

The null hypothesis of no difference between treatment groups in the mean change in LS-BMD Z-score at Month 12 relative to baseline. In testing this hypothesis, it is assumed that the standard deviations for the two treatment groups is 0.93 under  $H_0$  and  $H_A$ . Based on a primary endpoint of the change in LS-BMD Z-score at 12 months relative to baseline assuming a 0.63 increase in LS-BMD Z-score over 12 months with zoledronic acid and no change in the LS-BMD Z-score in the placebo group and a common standard deviation of 0.93, 82 patients are required to show a significant increase in LS-BMD Z-score at the 0.05 level with 85% power. Adjusting for a dropout rate of 10%, approximately 46 patients per treatment group are required.

The amount of information from controlled trials in a pediatric GIO population is limited. The 0.63 increase in LS-BMD Z-score is based on the increase observed with pamidronate-treated children on chronic glucocorticoid therapy presented in (Acott et al 2005). The common standard deviation of 0.93 was estimated from the pamidronate-treated children and untreated control evaluated in (Acott et al 2005). This standard deviation is consistent with the estimate of the standard deviation obtained from the zoledronic acid group of pediatric osteogenesis imperfecta patients in Study CZOL446H2202. Therefore, it is inferred that the assumption of a 0.63 increase in LS-BMD Z-score over 12 months with ZOL is acceptable.

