Adverse event tables will be sorted alphabetically by system organ class and then according to decreasing frequency of preferred term in the zoledronic acid group. If only system organ classes or preferred terms are presented, these will be sorted according to the decreasing frequency in the zoledronic acid group.

The following sets of adverse events will be summarized:

- All adverse events (by primary system organ class and preferred term)
 - Adverse events suspected to be related to study drug (by primary system organ class and preferred term)
 - Adverse events that occurred after first infusion and before second infusion (by primary system organ class and preferred term)
 - Most frequent adverse events (at least 5% in any group) (by primary system organ class and preferred term)
 - All adverse events (by primary system organ class, preferred term and maximum severity)
 - All adverse events (by underlying disease group, primary system organ class and preferred term)
 - Adverse events that result in death (by primary system organ class and preferred term)
 - Serious adverse events (by primary system organ class and preferred term)
 - Adverse events causing permanent discontinuation of study drug (by primary system organ class and preferred term)
 - Adverse events associated with a change in renal function (by preferred term). Time to first adverse event associated with a change in renal function will be presented separately.
- [REDACTED]
- Hypocalaemia adverse events (by preferred term). Time to first hypocalaemia occurrence based on AE and central lab calcium will be presented separately.

Incidence of risk as defined in the case retrieval strategy, during the study period, will be summarized by treatment group, and MedDRA levels. Relative risk of zoledronic acid group

vs. placebo will be presented along with corresponding 95% confidence intervals using the Mantel-Haenszel test.

Missing date convention

Partial AE start dates: If an AE start date is completely missing, then no imputation is implemented. AEs with completely missing start dates will be treated as treatment emergent. If the year of an AE start date is missing but the month is available, then the date will be imputed as the start date of the first study drug infusion + 1.

If the year is not missing and the month is missing, then date will be imputed as follows:

- If the AE year is less than the year the study drug infusion was administered, then July 1st of the year will be used.

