Adverse events associated with change in renal function are defined based on predefined search list which describe a clinically significant change in renal function. A search of the clinical trial database will occur based on this pre-specified list of MedDRA preferred terms. These adverse events will be summarized by preferred term. In addition, the event rate and 25th percentile (95% CI) of time to first adverse event associated with change in renal function will be summarized. The hazard ratio and 95% CI based on a Cox proportional hazards model with treatment as a factor will be presented. Between-treatment differences in time to first adverse event associated with change in renal function will be evaluated using the log-rank test. If a patient experiences an adverse event associated with change in renal function, the event time is defined as the earliest of all events if there are multiple. Otherwise, a patient is considered censored at the last contact date. Kaplan-Meier estimates will be plotted over time if at least 1% of overall population has experienced the event.

Patient listings will be provided for all adverse events associated with clinically significant change in renal function.

Hypocalcaemia adverse events and laboratory events

Hypocalcaemia adverse events will be searched based on preferred term and summarized. Patients with reported laboratory measurements associated with a signal of hypocalcaemia will be summarized by visit. Lab hypocalcaemia (low serum calcium levels) is present if the value of serum calcium from central lab is less than the lower limit of normal range provided by the central lab.

The number and percentage of patients who met these criteria will be summarized by treatment group overall.

The event rate and 25th percentile (95% CI) of time to first hypocalcaemia occurrence based on AE and central lab calcium will be summarized. The hazard ratio and 95% CI based on a Cox proportional hazards model with treatment as a factor will be presented. Between-treatment differences in time to first hypocalcaemia occurrence based on AEs and central lab will be evaluated using the log-rank test. If a patient experiences a hypocalcaemia and low calcium value based on the central lab, the event time is defined as the earlier of these events. Otherwise, a patient is considered censored at the last contact date. Kaplan-Meier estimates will be plotted over time if at least 1% of overall population has experienced the event.

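### The relative risk, hazard ratio and 25th percentile planned for renal, hypocalcaemia and other identified risks have no fallback for sparse events, so at about 46 per arm an effect estimate with a confidence interval may be lost

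*SAP*

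**What the plan says.** The SAP section on adverse events plans, for risks in the case retrieval strategy, an incidence by arm and a relative risk of zoledronic acid "vs. placebo will be presented along with corresponding 95% confidence intervals using the Mantel-Haenszel test". The list of those risks is not in the documents.

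For renal events the SAP says that "the event rate and 25th percentile (95% CI) of time to first adverse event associated with change in renal function will be summarized". It adds a Cox hazard ratio with 95% CI and a log-rank test. The same set is planned for hypocalcaemia, where an event is an adverse event or any central-laboratory calcium below the lower limit of normal. The only event threshold is for a graph: "Kaplan-Meier estimates will be plotted over time if at least 1% of overall population has experienced the event".

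There is no zero-cell rule, minimum event count, exact or penalised method, or risk difference. The CI in the sentence on the 25th percentile attaches to the percentile, not to the event rate.

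Protocol section 2.2, item 9, reads: "The safety objective is to demonstrate that zoledronic acid is safe for the treatment of osteoporotic children treated with glucocorticoids", through monitoring of clinical and laboratory parameters. No margin, hypothesis or precision target goes with it. The sample size (Protocol 9.8) rests on bone density alone.

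**The concern.** A ratio needs events in both arms. If the drug raises a risk that is rare without it, a likely pattern in a small trial is a few events on zoledronic acid and none on placebo. In that pattern the planned relative risk and hazard ratio have no finite value. The two statistics meant to size the harm can therefore fail in the direction that matters most for safety.

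The 25th percentile exists only where at least a quarter of an arm has the event. For an uncommon harm the table will say not reached, whatever the data.

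With no events in either arm, none of the comparative statistics can be computed. Beside an objective worded as demonstrating safety, an empty table could be read as proof, when 46 exposed children exclude only fairly high rates.

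**Working it through.** **Arm size.** Protocol 9.8 gives a difference of 0.63, SD 0.93, two-sided alpha 0.05 and 85% power. Normal approximation: 2 × (1.960 + 1.036)² × 0.93² / 0.63² = 39.1, so 40 per arm. A t-test has 84.9% power at 40 per arm and 85.8% at 41, so 41 per arm, or 82 in total, matches the plan. Then 82 / 0.90 = 91.1, rounded up to 92, or 46 per arm. This reproduces the stated figure. The steps below use n = 46.

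**Rates.** The only renal figure in the documents is 9% to 13% for acute kidney injury in adults (Protocol 3.6), where the bisphosphonate-induced form is called undocumented in children. No hypocalcaemia rate is given. All other rates below are assumptions.

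**Relative risk and hazard ratio.** With no placebo event the denominator of the relative risk is zero, with or without stratification. Cox fits on constructed data with 3, 5 and 6 events against 0 diverged: log hazard ratio about 24 to 27, standard error about 90,000 or more.

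P(no placebo event) = (1 − p)^46:

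| Placebo rate | P(0 of 46) |
|---|---|
| 1% | 63% |
| 2% | 39% |
| 3% | 25% |
| 5% | 9% |
| 9% | 1.3% |

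P(all events on zoledronic acid) = (1 − p0)^46 × [1 − (1 − p1)^46], with p0 on placebo and p1 on zoledronic acid:

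| p0 | p1 | Probability |
|---|---|---|
| 1% | 5% | 57% |
| 1% | 10% | 62% |
| 2% | 5% | 36% |
| 2% | 9% | 39% |
| 5% | 10% | 9% |

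**25th percentile.** Without censoring, the Kaplan-Meier curve must fall to 0.75 or below. Eleven events leave 35/46 = 0.761; twelve leave 34/46 = 0.739. So 12 of 46 are needed. The binomial probability of 12 or more is:

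| True rate | P(12 or more of 46) |
|---|---|
| 9% | 0.06% |
| 13% | 1.3% |
| 20% | 20% |
| 30% | 77% |

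**What remains at 4 against 0.** The log-rank test stays defined: observed minus expected 2.03, variance 1.00, p = 0.042 (Fisher's exact p = 0.117). The risk difference is 4/46 = +8.7 percentage points. Its 95% CI is 0.6 to 20.4 by Miettinen-Nurminen and −0.6 to 20.3 by Newcombe. So an interval is available, but its lower limit depends on the method.

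**What 0 of 46 excludes.** The upper limit is 1 − 0.05^(1/46) = 6.3% (one-sided 95%) or 1 − 0.025^(1/46) = 7.7% (two-sided 95%). A harm with a true rate of 1% is missed altogether with probability 0.99^46 = 63%.

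**The case against.** The strongest reply is that the plan does not leave such a signal unanalysed. The log-rank test works when every event is on one arm. Counts and percentages by arm, event rates, Kaplan-Meier plots and patient listings are all planned. A split of 4 against 0 would be visible and tested; only the ratio cells would be blank. This stands.

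Sparsity is also not established. The hypocalcaemia endpoint takes in any low central-laboratory calcium, with a sample scheduled 10 days after each infusion. The protocol calls only the symptoms rare. For renal events, the remark about children concerns bisphosphonate-induced injury and says nothing about the placebo rate of a predefined term list, in a population that may include lupus and nephrotic syndrome. This stands too: at a 5% placebo rate the chance of no placebo event is 9%, and at 9% it is 1.3%.

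That the relative risk covers renal and hypocalcaemia events is an inference, because the case retrieval strategy is not available. The hazard-ratio problem does not depend on it.

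The safety objective does have analyses behind it: adverse events, laboratory changes and shifts, GFR, notable values and vital signs. What it lacks is a criterion by which safety would count as demonstrated. The 1% threshold governs a plot and does no harm.

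None of this supplies a fallback when an arm has no event.

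**Conclusion.** The gap is real and modest. If placebo risk is 1% to 2%, the relative risk and hazard ratio have no finite estimate in 39% to 63% of trials of this size because placebo has no event. At 5% this falls to 9%. For renal events the 25th percentile is almost certain not to be reached, even at the adult rates. These figures assume 46 treated per arm and, for the percentile, no censoring; the placebo rates are assumptions.

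A reader might infer that these statistics are bound to fail, that a signal confined to zoledronic acid would go unreported, or that the safety objective has no analysis. The documents support none of these. They give no event rates for these children, hypocalcaemia may be common enough for every planned statistic, and the log-rank test, counts and listings would show the signal. What may be lost is an effect estimate with a CI. Separately, for uncommon events the trial can estimate safety but cannot demonstrate it.

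**What to change.** In the SAP, before unblinding:

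- For each case-retrieval-strategy risk, and for renal and hypocalcaemia events, report the rate per arm with an exact 95% CI and the risk difference with a score-based 95% CI. Miettinen-Nurminen is one suitable choice; name one method, since the lower limit at small counts depends on it.
- Present the relative risk and hazard ratio only when both arms have events. Keep the log-rank test.
- Replace the 25th percentile by Kaplan-Meier cumulative incidence at Month 6 and Month 12, with the cut days stated. Any earlier time point must fall late enough to include the Visit 3 sample. That sample is scheduled 10 days after the first infusion with no visit window, and the SAP counts the infusion day as Day 1, so a cut at Day 10 could miss it.

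Beside protocol objective 9, state that 0 of 46 events excludes only rates above 6.3% (one-sided 95%) or 7.7% (two-sided 95%), and that for uncommon events the trial estimates safety.

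The cost is some SAP text, a few table rows and a less favourable safety statement. No new data are needed.

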### **3 Investigational plan**

#### **3.1 Study design**

This will be an international, multicenter, randomized, double-blind, placebo controlled efficacy and safety study recruiting osteoporotic children and adolescents receiving glucocorticoid therapy within the 12 months preceding screening who manifest a LS-BMD Z-score of -0.5 or worse plus evidence of low impact/fragility fracture.

At the baseline visit (Visit 2), patients whose eligibility is confirmed will be randomized to one of two treatment groups. Patients may be hospitalized at the discretion of the investigator for observation following the first study drug infusion. Ionized calcium will be assessed before the first study drug infusion only. Patients will receive the second study drug infusion at the Month 6 visit. Safety and efficacy will be assessed at 6 and 12 months, with additional telephone visits to assess adverse events [REDACTED] and concomitant medication at 3 and 9 months. Renal safety utilizing the Schwartz calculation for GFR will be assessed at screening, and 10 days after the i.v. infusion of study drug 6 and 12 months.

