#### **5.5.7.1 Treatment of study drug related adverse events:**

As with other bisphosphonates, zoledronic acid has been associated with post-dose symptoms that may include fever, nausea, myalgia, arthralgia and bone pain, with onset occurring within the first 72 hours after the infusion. Typically these symptoms occur with the first infusion of bisphosphonate. The symptoms are usually mild to moderate and rarely severe. These symptoms may be adequately managed, at the discretion of the investigator, with non-steroidal anti-inflammatory agents (e.g. acetaminophen/paracetamol or ibuprofen) and/or anti-emetics by local treatment standards and according to approved local labeling. Based on data from controlled trials, treatment with non-steroidal anti-inflammatory agents will reduce the incidence of these symptoms by approximately 50%. In managing these symptoms it is important to encourage adequate hydration and food intake.

All dosages prescribed and dispensed to the patient and all dose changes during the study must be recorded on the concomitant medications/significant non-drug therapies CRF after start of study treatment.

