## 7 Safety monitoring

### 7.1 Adverse events

An adverse event (AE) is any untoward medical occurrence (e.g., any unfavorable and unintended sign [including abnormal laboratory findings], symptom or disease) in a subject or clinical investigation subject *after providing written informed consent* for participation in the study until the end of study visit. Therefore, an AE may or may not be temporally or causally associated with the use of a medicinal (investigational) product.

In addition, all reports of intentional misuse and abuse of the product are also considered an adverse event irrespective if a clinical event has occurred.

In this protocol, due to the long screening period (at least 4 weeks), although SAEs are collected from signing the informed consent, the AE page of the eCRF is only completed from the first day of study drug. In the case of randomized patients only, any events that occur prior to receiving study treatment, should be recorded in the eCRF as Medical History.

The occurrence of adverse events must be sought by non-directive questioning of the patient at each visit during the study. Adverse events also may be detected when they are volunteered by the patient during or between visits or through physical examination findings, laboratory test findings, or other assessments.

Abnormal laboratory values or test results constitute adverse events only if they fulfill at least one of the following criteria:

- they induce clinical signs or symptoms,
- they are considered clinically significant,
- they require therapy.

Clinically significant abnormal laboratory values or test results must be identified through a review of values outside of normal ranges/clinically notable ranges, significant changes from baseline or the previous visit, or values which are considered to be non-typical in patient with underlying disease. Investigators have the responsibility for managing the safety of individual patient and identifying adverse events. Alert ranges for laboratory and other test abnormalities are included in [Appendix 1](#).

Adverse events must be recorded in the Adverse Events CRF under the signs, symptoms or diagnosis associated with them, accompanied by the following information:

- the severity grade
  - mild: usually transient in nature and generally not interfering with normal activities
  - moderate: sufficiently discomforting to interfere with normal activities
  - severe: prevents normal activities

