- If the AE year is equal to the year the study drug infusion was administered, then the start date will be imputed as the start date of the first study drug infusion + 1.
- If the AE year is greater than the year the study drug infusion was administered, then the Jan 1st of the year will be used.

If the year is available and the month is non-missing, then the following rules will be applied relative to the month that study drug treatment was given:

- If the month in which the AE started is less than the month that the study drug infusion was administered, then:
 - If the AE year is less than or equal to the year the study drug infusion was administered, then the 15th day of the month will be used.
 - If the AE year is greater than the year the study drug infusion was administered, then the maximum of the first day of the month and the treatment start date + 1 will be used.
- If the month in which the AE started is equal to the month that the study drug infusion was administered, then:
 - If the AE year is less than the year the study drug infusion was administered, then the 15th day of the month will be used.
 - If the AE year is greater than or equal to the year the study drug infusion was administered, then the maximum of the first day of the month and the treatment start date + 1 will be used.
- If the month in which the AE started is greater than the month that the study drug infusion was administered, then:
 - If the AE year is less than the year the study drug infusion was administered, then the 15th day of the month will be used.
 - If the AE year is greater than or equal to the year the study drug infusion was administered, then the maximum of the first day of the month and the treatment start date + 1 will be used.

In case that the AE end date was completed, the AE start date imputed as above was after the AE end date, the AE start date was re-imputed using the AE end date.

Partial AE end dates: There is no STL convention to impute partial AE end date. Partial AE end date was imputed using (a) the last date of the month if only the day of AE end date is missing, (b) December 31 if only the year of AE end date is present. If a patient dies and the imputed end date is after the date of death, the date of death was imputed as the AE end date. When a patient dies, the end date for ongoing AEs was imputed using the date of death.

Adverse events associated with change in renal function

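### The rules for partial AE start dates name only the first infusion, and the rule for a missing year overrides a recorded month, so some events after the second infusion are dated before it

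*SAP*

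**What the plan says.** There are two infusions. Protocol 3.1 states: "Patients will receive the second study drug infusion at the Month 6 visit"; Table 6-1 puts that visit at Day 180.

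The SAP (Adverse events) lists a table of "Adverse events that occurred after first infusion and before second infusion". It also plans time-to-first-event analyses for renal adverse events and for hypocalcaemia. Each takes the earliest qualifying event, and for hypocalcaemia that is the earlier of the adverse event and the low central-laboratory value.

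The SAP's convention for partial AE start dates has three branches that matter here:

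- Year missing, month recorded. If the year is "missing but the month is available, then the date will be imputed as the start date of the first study drug infusion + 1".
- Month missing, year recorded. For an event in the same calendar year as the infusion, "then the start date will be imputed as the start date of the first study drug infusion + 1". If the AE year is later, 1 January of that year is used.
- Only the day missing, in or after the month of the first infusion: "then the maximum of the first day of the month and the treatment start date + 1 will be used".

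An imputed start that falls after a complete AE end date is moved back to the end date. A completely missing start date is not imputed, and the event counts as treatment-emergent. No branch mentions the second infusion.

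**The concern.** One planned table splits events at the second infusion, yet every floor in the convention is the first. In the year-missing branch this contradicts recorded data: a month that can only fall after the second infusion is replaced by the day after the first, which is Day 2 under the SAP's study-day rule. In the other two branches the record may not settle the order of event and infusion, but the rule still picks a side, often the earlier one. The end-date correction cannot offset this, because it only moves starts earlier.

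At stake is the description of safety by dose. Protocol 5.5.7.1 describes post-dose symptoms "with onset occurring within the first 72 hours after the infusion", so Day 2 is where genuine first-dose reactions are expected. A later event moved there overstates the first interval and shortens the time to a first renal or hypocalcaemia event. An imputed Day 2 hypocalcaemia event would also take precedence over a later, exactly dated laboratory value.

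The Day 2 default is not needed to keep such events treatment-emergent. Under Protocol 7.1, "the AE page of the eCRF is only completed from the first day of study drug".

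**Working it through.** The documents give no figure on this point, so there is none to reproduce. The check applies the rules to dates.

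**Inputs.** The first infusion is Day 1, the second is Day 180 (179 days later) and the final visit is Day 365 (Protocol Table 6-1). The rules are those of the SAP.

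**Assumptions.** First-infusion dates are spread evenly over the 365 days of a year. True onset is spread evenly over Days 181–365. The second infusion is on schedule. Where the SAP refers to the study drug infusion without saying which, it is read as the first; the phrase about the treatment start date supports this.

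**Example.** First infusion 10 March 2015, second 5 September 2015.

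| Recorded start | Imputed start | Against the second infusion |
|---|---|---|
| November, no year | 11 Mar 2015 | before, against the recorded month |
| September 2015 | 1 Sep 2015 | before; the record does not settle the order |
| October 2015 | 1 Oct 2015 | after, correct |
| 2015 only | 11 Mar 2015 | before; the record does not settle the order |
| 2016 only | 1 Jan 2016 | after, correct |

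In the first row only November 2015 lies between the first infusion and Day 365, so the month fixes the year. With infusions on 15 September 2015 and 12 March 2016, a start recorded only as 2016 becomes 1 January 2016, which is before the second infusion.

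**Full count.** 365 first-infusion dates × 185 onset days = 67,525 events that truly follow the second infusion. Of these, 5,399 start in its calendar month and 62,126 in a later month.

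1. Year missing: 67,525/67,525 = 100% are dated before the second infusion, including all 62,126 with a later recorded month.
2. Day missing: 5,045/5,399 = 93.4% within the second infusion's month, 0/62,126 = 0% in later months, and 5,045/67,525 = 7.5% overall.
3. Month missing:
   - Let d be the day of the year of the first infusion. Onset stays in the infusion year on 186 − d of the days for d = 1 to 185. The sum is 185 × 186/2 = 17,205 events, all set to Day 2.
   - The other 67,525 − 17,205 = 50,320 go to 1 January. That date precedes the second infusion when the first is on 7 July or later (d ≥ 188): 178 × 185 = 32,930 events, or 32,930/50,320 = 65.4%.
   - Total: (17,205 + 32,930)/67,525 = 50,135/67,525 = 74.2%.

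**Sensitivity of the day-missing rule.** If onset clusters just after the second infusion, the share misdated is 988/1,095 = 90.2% for Days 181–183 and 2,878/3,650 = 78.8% for Days 181–190.

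**Scale.** The share of partly dated events is not given. If it were 2–5% (an assumption) and all lacked only the day, then under even onset 0.02 × 7.5% = 0.15% to 0.05 × 7.5% = 0.37% of post-second-infusion events would move.

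**The case against.** The strongest reply is that this will seldom matter. Adverse events are asked about at every visit, including Day 190, ten days after the second infusion. Protocol 7.1 requires start and end dates, and Protocol 8.2 and 8.3 provide entry checks and queries. A reaction within 72 hours, asked about a week later, is unlikely to lack a day, and a month with no year should be rarer still. Protocol 5.5.7.1 adds that these symptoms typically follow the first infusion, so the clustering behind the 90.2% figure is the less expected case. Both arms use the same rules. Laboratory hypocalcaemia is also summarised by visit, independently of AE dates. The SAP does not say that imputed dates assign events to the between-infusions table, although it gives no other means of doing so.

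All of this stands, and it limits the size of the problem. It does not justify a rule that discards a recorded month.

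Two cautions about remedies also stand. Copying the first-infusion rule, that is, dating day-missing events to the second infusion plus one day, would reverse the error for events earlier in that month. With infusion day and onset both even over a 30-day month, that is 29/60 = 48%. And visits are only as close to the designated day as possible, so follow-up can exceed 12 months and a calendar month can occur twice.

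**Conclusion.** The point holds as a minor defect. The year-missing rule is wrong as written. The day-missing and month-missing rules leave a gap around the second infusion.

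A reader might go further and infer that partly dated events after the second infusion are in general dated before it, even against the recorded month. The documents do not support that. The day-missing rule never overrides a recorded month and places every later month correctly; only the year-missing rule overrides one. Nor do all branches favour the first interval, because month-missing events in a later year go to 1 January, which may fall on either side. And 93.4% is not the overall size of the day-missing error: it applies only within the second infusion's own calendar month.

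The percentages rest on even infusion and onset dates and an on-schedule second infusion. They are shares of partly dated events of each type, not of all events. What can change is the between-infusions table and the time-to-first renal and hypocalcaemia analyses.

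**What to change.** Revise the SAP's convention for partial AE start dates as follows, and state which infusion is meant wherever the text now leaves it open.

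(a) Month known, year missing: take the year in which that month falls between the first infusion and the last visit, then apply the day-missing rule. If the month occurs twice in that span, use the AE end date to choose; if that does not decide it, keep the current default.

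(b) Day missing in the second infusion's month, or month missing: use the AE end date first. If the order is still unresolved, count the event as treatment-emergent in the overall tables, report the number of such events in a footnote to the between-infusions table, and show that table with these events assigned to each interval in turn.

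The cost is SAP wording, slightly more programming and one footnote. No data collection changes.
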